## 4.4.1 Analysis of Primary Efficacy Variable

The primary efficacy variable is the composite clinical and histological response of the subject's Main Target Lesion as assessed 12 weeks after the start of the last PDT cycle that included treatment of the Main Target Lesion (Visit 5 or Visit 8). A Main Target Lesion with a complete clinical and histological response is defined as a completely cleared Main Target Lesion, i.e. if both lesion status is documented as 'Cleared' and question 'Is the main target lesion histologically cleared?' is answered with 'Yes' at corresponding visit. Not cleared clinical or histological lesion (status not 'Cleared' or question answered with 'No'), Unknown or missing data will be considered as not completely cleared Main Target Lesion (non-response). The primary null hypothesis (H01, one-sided) is that the complete clinical and histological response of the subject's Main Target Lesion assessed 12 weeks after the start of the last PDT cycle for subjects treated with BF-200 ALA is equal or lower to that of subjects treated with vehicle:

 $H_{01}$ :  $r_{ALA} \leq r_{vehicle}$ 

[figure not shown]
where rALA denotes the complete clinical and histological response rate of the subject's Main Target Lesion in the BF-200 ALA group and rvehicle denotes the complete clinical and histological response rate of the subject's Main Target Lesion in the vehicle group.

The primary alternative hypothesis ( $H_{11}$ , one-sided) is that the complete clinical and histological response rate of the subject's Main Target Lesion assessed 12 weeks after the start of the last PDT cycle for subjects treated with BF-200 ALA is superior to the complete clinical and histological response rate of the subject's Main Target Lesion for subjects treated with vehicle:

#### $H_{11}$ : $r_{ALA} > r_{vehicle}$

Superiority of BF-200 ALA in comparison to vehicle is established if the primary null hypothesis can be rejected. A Cochran-Mantel-Haenszel Test will be used to test the primary hypothesis on a significance level of 0.1% ( $\alpha$ =0.001; one-sided). As the CMH Test produces a two-sided p-value, if the direction of the observed common odds ratio supports the superiority outcome (e.g. common odds ratio > 1), the two-sided p-value will be converted to a one-sided p-value by dividing by two. Otherwise, the one-sided p-value will be calculated as 1 - (the two-sided p-value divided by two). Baseline number of lesions (1 vs.  $\geq$ 2 lesion(s)) and center will be used as stratification factors. A one-sided 99.9% confidence interval (CI) for the Mantel-Haenszel common odds ratio will additionally be applied. The primary analysis will be performed on the FAS and will be repeated, in sense of sensitivity analyses, for the PPS. Additionally, a sensitivity analysis using only subjects without missing values (complete-case analysis) will be performed.

Frequency tables of clinical and histological response of the Main Target Lesion will be presented by treatment group and visit.

As additional analyses, the primary efficacy variable will be analyzed descriptively by sex, age group I, Fitzpatrick skin type group, number of target lesions at baseline, location of Main Target Lesion, baseline size of Main Target Lesion, and center. Subgroup analyses will be conducted both for the PPS and FAS. Frequencies by treatment group and visit for each subgroup category and two-sided exact 95% CI for the difference in response rates will be calculated.

### 4.4.2 Analysis of Key Secondary Efficacy Variables

After the test of the primary efficacy variable is passed, the key secondary efficacy endpoints will be tested for differences between BF-200 ALA and vehicle. The corresponding null and alternative hypotheses to be tested are

 $H_{0i}: \theta_{ALA} \le \theta_{vehicle}$  vs.  $H_{1i}: \theta_{ALA} > \theta_{vehicle}$  (i = 2, ...)

where  $\theta$  denotes the population parameters associated with the respective key secondary endpoint.

Following the hierarchical testing strategy, the key secondary null hypotheses will only be tested if the first primary null hypothesis has been rejected and will be done strictly in the given order to ensure the family-wise error rate (FWER). Each subsequent test of a key secondary endpoint is conducted only if the preceding test was statistically significant on the planned one-sided alpha level of 0.001. Confirmatory hypothesis testing in the pre-defined order will stop once the first non-significant test result is obtained.

The key secondary efficacy analysis will be performed on the FAS and will be repeated, in the sense of sensitivity analyses, for the PPS.

Key secondary endpoint 1: Main Target Lesion clinical response (according to clinical assessment only) assessed 12 weeks after the start of the last PDT cycle.

Main Target Lesion clinical response is defined as response of the Main Target Lesion according to clinical assessment only.

The Main Target Lesion clinical response 12 weeks after the start of the last PDT cycle will be analyzed using a Cochran-Mantel-Haenszel Test (incl. confidence interval) with baseline number of lesions (1 vs.  $\geq$ 2 lesion(s)) and center as stratification factors.

Frequency tables of clinical response of the Main Target Lesion will be presented by treatment group and visit.

As additional analyses, the Main Target Lesion clinical response 12 weeks after the last PDT cycle will be analyzed descriptively by baseline size of Main Target Lesion and location of Main Target Lesion. Frequencies by treatment group and visit for each subgroup category and two-sided exact 95% CI for the difference in response rates will be calculated.

Key secondary endpoint 2: Main Target Lesion histological response (according to histological assessment only) assessed 12 weeks after the start of the last PDT cycle.

Main Target Lesion histological response is defined as response of the Main Target Lesion according to histological assessment only.

The Main Target Lesion histological response 12 weeks after the start of the last PDT cycle will be analyzed using a Cochran-Mantel-Haenszel Test (incl. confidence interval) with baseline number of lesions (1 vs.  $\geq$ 2 lesion(s)) and center as stratification factors.

Frequency tables of histological response of the Main Target Lesion will be presented by treatment group and visit.

As sensitivity analysis additionally a complete case analysis will be performed.

As additional analyses, the Main Target Lesion histological response 12 weeks after the last PDT cycle will be analyzed descriptively by baseline size of Main Target Lesion and location of Main Target Lesion. Frequencies by treatment group and visit for each subgroup category and two-sided exact 95% CI for the difference in response rates will be calculated.

29Jul2024

Key secondary endpoint 3: Subject complete clinical response (complete clearance of all target lesions according to clinical assessment only) assessed 12 weeks after the start of the last PDT cycle.

The subject complete clinical response is defined as complete clearance of all target lesions according to clinical assessment only.

The subject complete clinical response 12 weeks after the start of the last PDT cycle will be analyzed using a Cochran-Mantel-Haenszel Test (incl. confidence interval) with baseline number of lesions (1 vs.  $\geq$ 2 lesion(s)) and center as stratification factors.

Frequency tables of complete clinical responders will be presented by treatment group and visit.

As additional analyses, the subject complete clinical response 12 weeks after the last PDT cycle will be analyzed descriptively by location of lesions and number of lesions at baseline  $(1, \ge 2$  lesion(s)). Frequencies by treatment group and visit for each subgroup category and two-sided exact 95% CI for the difference in response rates will be calculated.

Key secondary endpoint 4: Subject complete response (clinically and histologically cleared Main Target Lesion (see above) and complete clinical remission of all Additional Target Lesions) assessed 12 weeks after the start of the last PDT cycle.

The subject complete response is defined as clinically and histologically cleared Main Target Lesion and complete response of all Additional Target lesions according to clinical assessment only. Only Main Target Lesion will be considered if no Additional Target lesions available.

The subject complete response 12 weeks after the start of the last PDT cycle will be analyzed using a Cochran-Mantel-Haenszel Test (incl. confidence interval) with baseline number of lesions (1 vs.  $\geq$ 2 lesion(s)) and center as stratification factors.

As sensitivity analysis additionally a complete case analysis will be performed.

Frequency tables of complete responders will be presented by treatment group and visit.

As additional analyses, the subject complete response 12 weeks after the last PDT\_cycle will be analyzed descriptively by location of lesions and number of lesions at baseline (1, ≥2 lesion(s)). Frequencies by treatment group and visit for each subgroup category and two-sided exact 95% CI for the difference in response rates will be calculated.

## 4.4.3 Analysis of Further Efficacy Variables

All further secondary efficacy variables will be analyzed descriptively and in an exploratory way. All analyses will be performed on the FAS and PPS. All statistical testing procedures will be done exploratory using a significance level of 5% ( $\alpha$ =0.05, two-sided).

Lesion complete clinical response rate per treatment arm (complete clearance of individual lesions (Main and Additional Target Lesions)) according to clinical assessment only, assessed 12 weeks after the start of the last PDT cycle.

The lesion complete clinical response rate is defined as the percentage of completely cleared individual lesions, in relation to the number of lesions at baseline (Visit 2).

The lesion complete clinical response rate per treatment arm 12 weeks after the start of the last PDT cycle will be analyzed descriptively. The absolute number of target lesions at baseline and the absolute and relative frequency of clinically cleared lesions 12 weeks after the start of the last PDT cycle will be tabulated per treatment arm.

As additional analyses, the lesion complete clinical response rate per treatment arm 12 weeks after the last PDT cycle will be analyzed descriptively by location of lesions and baseline size of lesions. Frequencies per subgroup category will be presented.

Main Target Lesion complete response (clinically and histologically cleared) assessed 12 weeks after PDT-1.

Main Target Lesion complete response is defined as response according to clinical and histological assessment.

The Main Target Lesion complete response 12 weeks after PDT-1 will be analyzed using a Cochran-Mantel-Haenszel Test (incl. confidence interval) with baseline number of lesions (1 vs.  $\geq$ 2 lesion(s)) and center as stratification factors.

As additional analyses, the Main Target Lesion complete response 12 weeks after PDT-1 will be analyzed descriptively by location of Main Target Lesion and baseline size of Main Target Lesion. Two-sided exact 95% CI for the difference in response rates will be calculated.

Main Target Lesion clinical response (according to clinical assessment only) assessed 12 weeks after PDT-1.

Main Target Lesion clinical response is defined as response according to clinical assessment only.

The Main Target Lesion clinical response 12 weeks after PDT-1 will be analyzed using a Cochran-Mantel-Haenszel Test (incl. confidence interval) with baseline number of lesions (1 vs.  $\geq$ 2 lesion(s)) and center as stratification factors.

As additional analyses, the Main Target Lesion clinical response 12 weeks after PDT-1 will be analyzed descriptively by location of lesions and baseline size of Main Target Lesion. Two-sided exact 95% CI for the difference in response rates will be calculated.

Main Target Lesion histological response (according to histological assessment only) assessed 12 weeks after PDT-1.

Main Target Lesion histological response is defined as response according to histological assessment only.

The Main Target Lesion histological response 12 weeks after PDT-1 will be analyzed using a Cochran-Mantel-Haenszel Test (incl. confidence interval) with baseline number of lesions (1 vs.  $\geq$ 2 lesion(s)) and center as stratification factors.

As additional analyses, the Main Target Lesion histological response 12 weeks after PDT-1 will be analyzed descriptively by location of lesions and baseline size of Main Target Lesion. Twosided exact 95% CI for the difference in response rates will be calculated.

Lesion complete clinical response rate per treatment arm (complete clearance of individual lesions (Main and Additional Target Lesions)) according to clinical assessment only, assessed 12 weeks after PDT-1.

The lesion complete clinical response rate per treatment arm is defined as the percentage of individual lesions in the respective treatment arm with complete clearance.

The lesion complete clinical response rate per treatment arm 12 weeks after PDT-1 will be analyzed descriptively. The absolute number of target lesions at baseline and the absolute and relative frequency of clinically cleared lesions 12 weeks after the start of the last PDT cycle will be tabulated per treatment arm.

Subject complete clinical response (complete clearance of all Target Lesions according to clinical assessment only) assessed 12 weeks after PDT-1.

The subject complete clinical response is defined as complete clearance of all target lesions according to clinical assessment only.

The subject complete clinical response 12 weeks after PDT-1 will be analyzed using a Cochran-Mantel-Haenszel Test (incl. confidence interval) with baseline number of lesions (1 vs.  $\geq$ 2 lesion(s)) and center as stratification factors.

Subject complete response (clinically and histologically cleared Main Target Lesion and complete clinical remission of all Additional Target Lesions) assessed 12 weeks after PDT-1.

The subject complete response is defined as clinically and histologically cleared Main Target Lesion and complete response of all Additional Target lesions according to clinical assessment only.

The subject complete response 12 weeks after PDT-1 will be analyzed using a Cochran-Mantel-Haenszel Test (incl. confidence interval) with baseline number of lesions (1 vs.  $\geq$ 2 lesion(s)) and center as stratification factors. For all Target Lesions, assessment of esthetic appearance by the investigator 12 weeks after the start of the last PDT cycle, but prior to surgical excision of the Main Target Lesion and any alternative treatment of Additional Target Lesions.

Esthetic appearance of the Main Target Lesion by the investigator will be assessed prior to surgical excision of this target lesion. Esthetic appearance of additional Target lesion(s) will be assessed at the end of the clinical observation period of the study (12 weeks after PDT-1 (Visit 5) or 12 weeks after PDT-3 if re-treated (Visit 8)). The esthetic appearance is assessed using the 4-point scale ranging from very good (0) to unsatisfactory (3).

The assessment of esthetic appearance by the investigator will be analyzed descriptively on a lesion basis. The absolute and relative number of very good / good / satisfactory / unsatisfactory / no answer assessments will be tabulated per treatment arm and visit.

Subjects' satisfaction regarding esthetic outcome and treatment 12 weeks after the start of the last PDT cycle, but prior to surgical excision of the Main Target Lesion or alternative treatment of Additional Target Lesions at the end of the clinical observation period.

Esthetic outcome of the Main Target Lesion will be assessed prior to surgical excision of this target lesion. Esthetic outcome of additional Target Lesion(s) as well as subjects' overall satisfaction with PDT treatment will be assessed at the end of the clinical observation period of the study (12 weeks after PDT-1 (Visit 5) or 12 weeks after PDT-3 if re-treated (Visit 8)). Satisfaction with esthetic outcome is assessed using the 4-point scale ranging from very good (0) to unsatisfactory (3). Subjects' overall satisfaction with PDT treatment is assessed by the question if the subject would choose the treatment again.

The subjects' satisfaction regarding esthetic outcome will be analyzed descriptively on a lesion basis. The absolute and relative number of very good / good / satisfactory / unsatisfactory / no answer assessments will be tabulated per treatment arm and visit.

The subjects' satisfaction regarding esthetic outcome and subjects' satisfaction with PDT treatment will be analyzed descriptively on a subject basis. If the subject has documented different satisfaction regarding esthetic outcome for different lesions, worst satisfaction will be considered for tabulation. The absolute and relative number of very good / good / satisfactory / unsatisfactory / no answer subject assessments of esthetic outcome as well as the answers to the question if the subject would choose the treatment again will be tabulated per treatment arm and visit.

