Non-responders or partial responders according to clinical assessment after the 1st PDT cycle, i.e., subjects with visible remaining target lesions at Visit 5 (Week 12 after PDT-1), will have the clinically remaining lesions retreated with a 2nd PDT cycle starting at Visit 5 (PDT-3). If the Main Target Lesion is clinically cleared at this time point, it will be excised at this Visit 5. PDT-4 will be applied 1-2 weeks later, at Visit 6. Subjects will then be contacted by phone 1 week ± 2 days after the 2nd PDT cycle ended, and attend two further visits for assessment of efficacy and safety (Visit 7: 5 weeks ± 1 week after PDT-3, and Visit 8: 12 weeks ± 1 week after PDT-3). At Visit 8, a final clinical assessment will be performed identifying complete clinical responders 12 weeks after the start of the 2nd PDT cycle and partial or non-responders, i.e., subjects still showing remaining target lesions after the 2nd PDT cycle. A retreated Main Target Lesion will be excised on this day, irrespective of the clinical outcome.

In general, clinically complete responders are categorized 12 weeks after the start of the last PDT cycle (PDT-1 or PDT-3) according to clinical assessment only and are defined as subjects with all Target Lesions (Main plus Additional Target Lesions) clinically cleared.

All subjects will receive excision of their Main Target Lesion, at the latest at Visit 8 for histopathological evaluation of lesion status. Along with the excision of the area of the Main Target BCC Lesion, the ink marks applied at Visit 2 will be removed. Any remaining Additional Target Lesions at Visit 8 will be treated at the discretion of the investigator following completion of final assessments of the clinical observation period.

For all subjects who completed the clinical observation period, four FU visits are scheduled (12 ± 1 months, 24 ± 2 months, 36 ± 2 months and 60 ± 2 months after completion of PDT cycle 1 (Visit 5)). All subject data listed in [Section 7.1](#) and results of assessments have to be recorded in the subject electronic case report form (eCRF). Data reported during the FU part of the study will be analyzed and reported separately and are not part of the clinical observation period of the study.

Inclusion and exclusion criteria

Main inclusion criteria:

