#### 3.5 Per-Protocol Set

The per-protocol set (PPS) consists of all subjects of the FAS without any major protocol deviations. The assignment of subjects to the treatment groups will be as actually treated.

Protocol deviations will be identified and classified for each subject during a blind data review (see section 4.8).

The following protocol deviations are a priori defined in the protocol to have a "major" grade and will lead to an exclusion from the PPS:

- The treatment differs significantly from protocol (e.g. incubation period differs by more than 30 min from times indicated by the protocol; distance of the lamp differs by more than 1 cm from the range indicated by the manual; illumination time differs by more than 20% (2 min) from the pre-defined illumination time of 10 min.
- □ Forbidden anti-inflammatory medication (within ± 7 days of PDT)
- Description Other forbidden medication will be decided on a case-by-case basis.
- □ Missing visits (with exception of Visit 4 or Visit 7 and Phone call 1 and Phone call 2)
- The interval between 2 PDT treatments of the same cycle exceeded the interval indicated by the protocol by more than 4 days.
- Treatment with a 2nd treatment cycle, although the lesion(s) has/have been clinically cleared already after the 1st treatment cycle.
- D Meeting any exclusion criteria throughout the treatment period of the study.

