## 3.7 Assignment of Analysis Sets to Analysis

The full analysis set will be considered the primary analysis set. The FAS will be the analysis set applied to the evaluation of primary, key secondary and further secondary endpoints.

The PPS will be used for sensitivity analysis of the primary, key secondary and further secondary endpoints.

The enrolled set and the randomized set are the analysis sets for the summary of subject disposition and discontinuation.

The SAF is the analysis set for all safety analyses.

All analyses based on FAS, PPS, enrolled and randomized set will be performed for planned treatment, i.e. by the treatment group to which they were randomized ("intention-to-treat"). All analyses based on SAF will be performed for actual treatment, i.e.by the treatment they received.

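### The single per-protocol set counts cycle-2 deviations, so for the six endpoints assessed 12 weeks after PDT-1 its membership depends on events after the outcome

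*SAP*

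**What the plan says.** SAP 3.5 defines one set: "The per-protocol set (PPS) consists of all subjects of the FAS without any major protocol deviations". Classification is per subject, not per cycle or endpoint: "Protocol deviations will be identified and classified for each subject during a blind data review". The listed deviations lead to exclusion without discretion, apart from other forbidden medication, which is decided case by case.

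The rules are not confined to cycle 1. Incubation time, lamp distance, illumination time and anti-inflammatory drugs around PDT apply to all four sessions. So does the spacing rule: "The interval between 2 PDT treatments of the same cycle exceeded the interval indicated by the protocol by more than 4 days". The visit rule reads "Missing visits (with exception of Visit 4 or Visit 7 and Phone call 1 and Phone call 2"), so missing Visit 6 or Visit 8 excludes a subject. A further rule is "Meeting any exclusion criteria throughout the treatment period of the study", and that period is longer for retreated subjects. One rule works the other way: it removes subjects retreated although already cleared.

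SAP 3.7 assigns the set broadly: "The PPS will be used for sensitivity analysis of the primary, key secondary and further secondary endpoints". SAP 4.4.3 repeats this for the further secondary endpoints: "All analyses will be performed on the FAS and PPS". SAP 2.3 lists six of these as assessed 12 weeks after PDT-1. The protocol (synopsis and 11.2) says only that the PPS may be used for selected further secondary analyses, and SAP 5 does not list the widening as a change.

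Under Protocol 5.1.2 and 7.2.2, subjects with all lesions clinically cleared finish at Visit 5, and only those with a remaining lesion enter cycle 2. For a partial responder, the protocol synopsis adds: "If the Main Target Lesion is clinically cleared at this time point, it will be excised at this Visit 5".

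**The concern.** A per-protocol set should be formed from events that can bear on the outcome being analyzed. The PDT-1 endpoints are fixed at Visit 5, so a PDT-4 given too late or a missed Visit 8 cannot change them. Yet either event removes the subject from the PPS analysis of those endpoints, and only a subject with a lesion left at Visit 5 (or one retreated by mistake) can have such an event. For subject complete clinical response after PDT-1, exclusion is therefore tied to the outcome itself.

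The protocol already recognizes the principle. Section 11.4 exempts missed Visits 4 and 7 because they have no bearing on the study outcome. Nothing in SAP 3.5, 3.7, 4.4.3 or 4.8 extends this to cycle-2 events when the endpoint is a cycle-1 endpoint. What is at stake is whether the PPS gives a fair sensitivity check on one-cycle efficacy.

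**Working it through.** **The plan's own figures.** The documents give no PPS size, deviation rate or cycle-1 response rate. The only planning rates (SAP 1.1) are 65% and 25%, for the composite endpoint after the last cycle, with 149 and 37 subjects. Their odds ratio is (0.65 × 0.75)/(0.35 × 0.25) = 5.57, against a stated 5.6. Power at one-sided alpha 0.001, ignoring strata, is 92.9% by normal approximation, consistent with the stated minimum of 90%. These rates are used below for illustration only.

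**Formula for subject complete clinical response after PDT-1.** Let r be the Visit 5 rate among subjects otherwise eligible for the PPS, d the share of Visit 5 non-responders removed for cycle-2 events, and c the share of Visit 5 responders removed for mistaken retreatment. Then

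r' = r(1 − c) / [r(1 − c) + (1 − r)(1 − d)].

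The PPS rate exceeds r exactly when d > c. If only deviations up to the Visit 5 assessment count, d = c = 0 and r' = r.

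**Equal d in both arms, c = 0, r = 65% and 25%:**

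| d | BF-200 ALA | Vehicle | Difference | Odds ratio |
|---|---|---|---|---|
| 0 | 65.0% | 25.0% | 40.0 | 5.57 |
| 5% | 66.2% | 26.0% | 40.2 | 5.57 |
| 10% | 67.4% | 27.0% | 40.3 | 5.57 |
| 20% | 69.9% | 29.4% | 40.5 | 5.57 |
| 30% | 72.6% | 32.3% | 40.4 | 5.57 |

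At d = 10%, about 5 of 52 BF-200 ALA non-responders (149 × 0.35) and 3 of 28 vehicle non-responders (37 × 0.75) are removed. With r = 50% and 15%, d = 10% gives 52.6% and 16.4%. With d = c = 10% the rates return to 65% and 25%.

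**Odds ratio.** With c = 0, each arm's odds are multiplied by 1/(1 − d), so the odds ratio is multiplied by (1 − d_vehicle)/(1 − d_ALA). Equal d leaves it unchanged. With d = 20% on BF-200 ALA and 10% on vehicle it becomes 5.57 × 0.90/0.80 = 6.27. Reversed, it becomes 5.57 × 0.80/0.90 = 4.95.

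**Rate difference, d = 15% in both arms.** The sign depends on the underlying rates:

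- 55% and 12% become 59.0% and 13.8%: +2.2 points.
- 65% and 25% become 68.6% and 28.2%: +0.4 points.
- 80% and 25% become 82.5% and 28.2%: −0.7 points.

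**The other five PDT-1 endpoints.**

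- *Subject complete response.* Subjects with every lesion clinically clear but positive histology are failures who never enter cycle 2. If half the failures are exposed and d = 10%, the BF-200 ALA rate is 66.2% rather than 67.4%. Same tendency, weaker.
- *Main Target Lesion complete, clinical and histological response.* Partial responders with a cleared Main Target Lesion also enter cycle 2, so responders are removed as well as non-responders. For the complete and histological versions, some failures are again never exposed. The documents do not fix the direction.
- *Lesion-level clinical response.* Removing a partial responder also removes that subject's cleared lesions. The direction is again not fixed, and this endpoint is only tabulated.

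**Primary and key secondary Main Target Lesion endpoints.** A partial responder whose Main Target Lesion was excised at Visit 5 can leave the PPS for a cycle-2 event that cannot affect that lesion. These lesions were clinically cleared, so they fail the composite only if histology is positive or missing. Removing them would tend to lower the PPS rate. Where the Main Target Lesion was retreated, cycle-2 deviations precede the outcome and exclusion is proper.

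**The case against.** The strongest reply is that little depends on these analyses. The FAS is the primary set, the PDT-1 endpoints are exploratory, and the PPS is a sensitivity set reported beside the FAS. That stands, and it limits the importance of the point.

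A reader might infer that the treatment effect after one cycle is inflated in the PPS. The documents do not support this. The specified inference is the Cochran-Mantel-Haenszel test with a common odds ratio, which equal exclusion rates leave unchanged, and the rate difference can move either way.

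A reader might also expect more cycle-2 deviations on BF-200 ALA because of pain. No such rate is given, and the text weakens the mechanism. Protocol 5.1.3 has the lamp continue after an interruption until the required time is reached, and it permits several pain measures. Interruption alone is not a listed major deviation. A higher rate on vehicle would lower the odds ratio.

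Nor can inflation be claimed for all six endpoints or for the primary endpoint, for the reasons shown in the working. The mistaken-retreatment rule also offsets some of the rise, although such retreatment should be rare.

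A last reply is that the blind data review will deal with it. SAP 4.8 does not say so: it repeats the same deviations and sets one PPS allocation. Blinding to treatment does not blind the review to Visit 5 response.

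**Conclusion.** The point holds for how the PPS is built. A stated rule removes subjects from the PPS analysis of the six PDT-1 endpoints for events after the outcome, and no passage corrects it. An upward shift in both arms is clear only for subject complete clinical response, provided d > c. Its size is about 1 to 8 points at rates of 65% and 25% with d from 5% to 30%. Those rates are borrowed from the last-cycle composite endpoint, and d is assumed. The tendency is weaker for subject complete response and of uncertain direction for the other four.

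Distortion of the odds ratio requires exclusion rates that differ by arm, and could go either way. Part of the PPS analysis of the primary and key secondary Main Target Lesion endpoints is also affected, probably downward. No FAS result changes. This is a biased sensitivity analysis worth correcting because the correction is cheap, not a threat to the trial's main conclusion.

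**What to change.** In SAP 3.5 and 4.8, define a second PPS flag, set at the blind data review, that counts only deviations up to and including the Visit 5 assessment. Use it for all six endpoints assessed 12 weeks after PDT-1. Use it also for the Main Target Lesion endpoints, including the primary, in subjects whose Main Target Lesion was excised at Visit 5. Keep the present PPS for everything else, including Main Target Lesions retreated in cycle 2 and subject-level endpoints after the last cycle. Refer to the flag in SAP 3.7 and 4.4.3 so that each analysis names its set.

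The cost is a short SAP addition, one extra flag and slightly more analysis work. It needs no new data and leaves the FAS analyses as they are.
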